9	DATA HANDLING AND RECORD KEEPING.....	14
9.1	CONFIDENTIALITY.....	14
9.2	SOURCE DOCUMENTS	15
9.3	CASE REPORT FORMS (AS APPLICABLE).....	15
9.4	RECORDS RETENTION.....	15
10	STUDY MONITORING, AUDITING, AND INSPECTING	15
10.1	STUDY MONITORING PLAN.....	15
10.2	AUDITING AND INSPECTING	15
11	ETHICAL CONSIDERATIONS	16
12	STUDY FINANCES	16
12.1	FUNDING SOURCE.....	16
12.2	CONFLICT OF INTEREST	16
12.3	SUBJECT STIPENDS OR PAYMENTS	16
13	PUBLICATION PLAN	16
14	REFERENCES	16
15	APPENDICES	20

List of Abbreviations

VHL – von Hippel-Lindau
CEUS – Contrast-enhanced ultrasound
US – ultrasound
CT – computed tomography
MRI – magnetic resonance imaging
RCC – renal cell carcinoma
NSF – nephrogenic sclerosing fibrosis
FDA – Food and Drug Administration
CPS – cadence pulse sequencing
BHD – Birt-Hogg-Dube syndrome
HLRCC – Hereditary Leiomyomatosis and Renal Cell Carcinoma
TSC – Tuberous Sclerosis Complex (TSC).

Study Summary

Title	Cross-Sectional Study of Contrast-Enhanced Ultrasound with Lumason/Definity as a Screening Tool for Kidney Cancer in Patients with Von Hippel-Lindau
Short Title	CEUS VHL
Protocol Number	LCCC1824
Phase	NA
Methodology	Cross-sectional Observational Study
Study Duration	12 months
Study Center(s)	UNC-CH
Objectives	To determine accuracy of CEUS for detection of malignancy kidney lesions in patients with Von-Hippel Lindau
Number of Subjects	15
Diagnosis and Main Inclusion Criteria	Von-Hippel Lindau, Birt-Hogg-Dube syndrome, Hereditary Leiomyomatosis, Renal Cell Carcinoma, or Tuberous Sclerosis Complex Key inclusion criteria: Undergoing kidney surveillance with MRI
Study Product, Dose, Route, Regimen	Microbubble contrast agent (IV infusion): 1. Perflutren Lipid Microspheres (Definity) 2. Sulfur hexafluoride Lipid (Lumason)
Duration of administration	15 minutes
Reference therapy	Contrast-enhanced MRI
Statistical Methodology	Kappa statistics

1 Introduction

This document is a protocol for a human research study. This study is to be conducted according to US and international standards of Good Clinical Practice (FDA Title 21 part 312 and International Conference on Harmonization guidelines), applicable government regulations and Institutional research policies and procedures.

1.1 Background

Von-Hippel Lindau (VHL) is one of several inherited familial syndromes that involves multiple organs and predisposes patients to the development of various benign and malignant tumors in these organs, including the central nervous system (CNS), kidney, pancreas, and adrenal glands. Renal Cell Carcinoma (RCC) is the leading cause of death in patients with VHL. Approximately two-thirds of patients with VHL will develop kidney cysts, and the frequency of RCC varies from 25-70% depending on age¹. The Bosniak criteria, a classification system used to classify kidney cysts, is used to define the cystic lesions present in VHL. The Bosniak criteria are typically applied to contrast-enhanced CT or MRI. Consequently, surveillance guidelines recommend screening with yearly ultrasound and every other year contrast-enhanced MRI². Other familial syndromes at risk of kidney cancer that require routine lifelong imaging surveillance include Birt-Hogg-Dube syndrome (BHD), Hereditary Leiomyomatosis and Renal Cell Carcinoma (HLRCC) and Tuberous Sclerosis Complex (TSC).

The mean age of diagnosis of RCC in VHL is 40 years³, but atypical presentations have occurred in patients as young as 16⁴. Therefore, VHL Alliance Screening Guidelines recommend beginning active surveillance with yearly ultrasound and every other year contrast-enhanced MRI at age 16². In addition to abdominal imaging, CNS MRI using contrast is recommended every 2-3 years². Therefore, patients that live to their 70s may be exposed to >50 contrast-enhanced MRI scans in a lifetime. Routine imaging surveillance is also a major component of management in BHD, HLRCC and TSC at variable screening intervals.

Gadolinium was once considered a very safe contrast agent for MRI with a low adverse event rate and much lower rates of allergic response compared to iodinated contrast used with CT. In 2006 a disease called Nephrogenic Sclerosing Fibrosis (NSF), a devastating disease leading to fibrosis of various organs, was described and found to be highly correlated with the use of gadolinium in patients with impaired kidney function^{5,6}. Changes in prescribing practices led to the elimination of NSF, but a new entity, Gadolinium Deposition Disease, is now described in which dose-related gadolinium deposition was found in the brains of autopsy patients receiving gadolinium but not controls^{7,8}. Although the clinical significance of this is not yet clear, avoidance of multiple repeated doses of gadolinium and costly MRI tests may benefit any patient, but particularly those requiring large lifetime doses.

Contrast-enhanced ultrasound (CEUS) is an emerging imaging technology that is being investigated for use in characterizing indeterminate kidney lesions⁹. Thus far, results have shown excellent sensitivity and moderate specificity, both comparable to contrast-enhanced CT and MRI. Microbubbles, the contrast agent used in CEUS have thus far proven to be quite safe based on decades of clinical use in cardiac imaging¹⁰. The rate of allergic reaction is similar to gadolinium, and microbubbles are not nephrotoxic. For certain patients, replacement of contrast-enhanced MRI with CEUS may significantly reduce lifetime exposure to gadolinium as well as costs associated with an expensive test.

1.2 Investigational Agent

Contrast-Enhanced Ultrasound Diagnostic Imaging of the Kidney

Ultrasound (US) imaging of the kidney is typically performed in the United States without contrast as no US contrast agent is currently approved for this indication. Without contrast, malignant tumors often cannot be definitively differentiated from benign tumors or pseudotumors. For this reason, following the identification of a kidney lesion via US without contrast, contrast-enhanced CT or MRI is then performed to stage and grade the lesion.

US contrast agents are gas-filled microbubbles which are intravenously administered in very small volume boluses or slow infusions. These microbubbles typically have mean diameters between 1 to 6 μm , remain

intravascular for several minutes, and do not diffuse into the interstitium (pure blood-pool agents)¹¹. Three US contrast agents are Food and Drug Administration (FDA) approved for human use: perflutren lipid microspheres (Definity®), sulfur hexafluoride lipid microspheres (Lumason®) and perflutren protein-type A microspheres (Optison®). All are FDA indicated for use in cardiac studies, and Lumason® is also FDA approved for liver and urinary tract imaging. The intent of this study is not to change the labeling of either FDA-approved agent.

Contrast Agents

Definity® (perflutren lipid) is an FDA-approved US contrast agent indicated to opacify the left ventricular chamber and to improve the delineation of the left ventricular endocardial border in patients with sub-optimal echocardiograms. It is activated by mechanical agitation with a Vialmix® which produces a milky white injectable suspension of perflutren lipid microspheres composed of octafluoropropane. Activated perflutren may be injected by either an intravenous bolus or infusion. See <http://www.accessdata.fda.gov/scripts/cder/drugsatfda/> for full prescribing information. When used in this setting, the maximum dose of perflutren is administered as either bolus doses or one single intravenous infusion.

Lumason® (sulfur hexafluoride lipid) is an FDA-approved US contrast agent indicated for use in adult patients with suboptimal echocardiograms to opacify the left ventricular chamber and to improve the delineation of the left ventricular endocardial border and with ultrasound of the liver in adult and pediatric patients to characterize focal liver lesions. See http://www.accessdata.fda.gov/drugsatfda_docs/label/2016/203684s001lbl.pdf for full prescribing information.

Associated Toxicities

Most safety studies have been performed in cardiac patients as this was the only FDA approved indication until April 4, 2016 when Lumason® was approved for liver applications. Thus far, microbubble agents have been shown to be quite safe^{12,13}. In pre-market clinical trials, 1716 subjects were evaluated with activated perflutren lipid. Of the 1716 subjects, 144 (8.4%) had at least one treatment-related adverse reaction. There were 26 serious adverse events and 15 (0.9%) subjects discontinued because of an adverse event, 1 due to a hypersensitivity reaction and the rest due to dizziness, chest pain, dyspnea or back pain. The events appeared within 1 – 15 minutes of the drug administration and were of moderate intensity resolving usually without treatment within minutes or hours after onset. Of the 11 other serious adverse events, which appeared within 2-15 days of the drug administration, all appeared to be a progression of underlying cardiac and non-cardiac disease. Nineteen subjects (1.1%) suffered serious cardiopulmonary adverse events including 8 deaths. The deaths occurred several days after activated perflutren lipid administration and appear to be related to the course of underlying disease.

For all AEs, there were no differences in the overall incidence based on age, gender, or route of administration. The most common events were (% of patients experiencing): headache (2.3%), back and renal pain (1.2%), flushing (1.1%) and nausea (1.0%).

Initial post-marketing experience, which included over 1 million patients with 5 years surveillance, showed the only medically significant risk was rare allergic events, occurring at a rate of 1 in 10,000¹³.

Cardiopulmonary Reactions^[14]

Cardiopulmonary contraindications include cardiac shunts and hypersensitivity to perflutren. The initial mandated 30-minute monitoring period was limited to patients with pulmonary hypertension or unstable cardiopulmonary conditions. The mandatory 30-minute monitoring period was removed in 2011, although a statement remained that most serious cardiopulmonary reactions occur within 30 minutes of administration. For this reason, the label states that cardiopulmonary resuscitation personnel and equipment be readily available prior to perflutren administration, and that all patients be monitored for acute reactions.

Although recent studies have shown no increased risk in patients with pulmonary hypertension¹⁴, patients with a history of known cardiac shunts, pulmonary hypertension or unstable cardiopulmonary conditions

will be excluded from our study. In addition, any patient with a suspected reaction during imaging will be monitored 30-minutes post-contrast agent administration by clinical or research nurse.

Hypersensitivity Reactions

Anaphylaxis to perflutren is extremely rare, however, in case of a severe reaction, EpiPen® (epinephrine) injections will be kept near the US machine for all patients.

High Ultrasound Mechanical Index (MI)

While high ultrasound MI of the heart may cause microbubble cavitation and subsequent ventricular arrhythmias, this was seen only at MI>1.6, higher than the typical MI used for microbubble disruption, with an agent no longer in clinical use.¹⁵ No premature ventricular contractions were seen with MI≤1.1. Large clinical trials using MI≤1.0 for expanded cardiac indications have shown no significant concerns for arrhythmias^{13,16,17,13,16,17}

Nevertheless, the safety of perflutren at MIs >0.8 has not yet been established by the manufacturer. However, real-time measurement of renal blood flow in 19 healthy subjects using perflutren was reported, using a flash replenishment high-MI (MI of 1.0) US technique. The contrast agent was well tolerated with no serious adverse events. One patient each had a 20mmHg increase in systolic blood pressure, a very brief and mild episode of flushing, and mild back pain, but no cardiac arrhythmias were recorded during the study period¹⁸. A second study using Sonovue® contrast agent with flash-replenishment high-MI to detect changes in kidney perfusion via US in 10 normal volunteers reported the agent was well tolerated, and not associated with any adverse events¹⁹.

Small pre-clinical studies performed in rodents and pigs²⁰⁻²³ showed conflicting results. One group showed glomerular capillary hemorrhage in exposed animals while other groups showed no sign of damage. The clinical relevance of these findings has not yet been investigated and is believed to be minimal, if any.

1.3 Preclinical Data

Numerous pre-clinical studies of CEUS have been performed, primarily in rodent kidneys but also larger animals like rabbit and pig, that investigate overall perfusion of diseased kidneys²⁴⁻²⁶ or kidneys exposed to various medications^{27,28}. In the field of oncology, many pre-clinical studies have been performed to determine the sensitivity of CEUS for detection of malignancy²⁹⁻³¹. The use of targeted microbubbles (with antibodies attached to the microbubble surface) has been investigated in this field as well^{32,33}.

1.4 Clinical Data to Date

Advancements in imaging technique combined with the nonlinear properties of microbubbles have spurred the development of contrast-specific US techniques such as CPS (Contrast Pulse Sequencing). Such imaging techniques provide high-resolution images of tissue vasculature and allow the assessment of the microcirculation patterns in real-time³⁴⁻⁴⁰. Outside of the United States, or in the context of clinical trials, US contrast agents have been used in kidney imaging^{36,37,40-44}. Levovist® (lipid and galactose microparticle suspension) and Sonovue® (lyophilized sulfur hexafluoride microbubbles), two non-FDA approved similar US contrast agents approved for use in countries outside of the United States, have been used in the general population to identify and diagnose kidney pseudotumors⁴⁵, cystic kidney lesions^{37,41,43,46}, and solid kidney lesions^{40,44}.

In the United States, where there has been significantly less research on using US contrast in humans, the US contrast agent, Definity®, was used in one study to measure renal blood flow in a healthy population¹⁸, effectively reproducing previous animal studies in the human population. Multiple contrast agents were used in a large retrospective study of CEUS in patients with kidney lesions⁴⁷ and showed excellent sensitivity (100%) and specificity (99%). Since that study, several smaller studies in the United States have looked at CEUS in the kidney and consistently shown excellent sensitivity^{48,49}. Studies outside the United States show similar sensitivities and specificities^{9,50}.

1.5 Dose Rationale and Risk/Benefits

Dosages for both Definity and Lumason are based on package inserts, expert opinion from radiologists who routinely use CEUS for kidney imaging, and our previous experience from clinical trials (IRB 12-2314, 15-1866, 17-1130). Because the kidney is a very vascular organ, use of 0.2mL Definity has been adequate for visualization of lesion enhancement. Our experience has been with both bolus doses of 0.2mL and infusion at set rates based on BMI. The infusion rate can be increased or decreased if visualization is not adequate. Use of either small boluses or infusion allows for multiple injections for patients with multiple lesions. Patients with greater abdominal girth and multiple lesions may require a 2nd dose as their bolus doses or rate of infusion will be higher. In the case of a 2nd dose, a 30-minute interval between injections will be instituted. All microbubble contrast agents are injected intravenously.

The greatest risk is of an unknown hypersensitivity reaction to the microbubbles as many patients will not have previous exposure to these contrast agents. However, the rate of true allergic reactions is low and similar to that for gadolinium-based contrast agents. Other risks are transient and resolve when the contrast agent is cleared. Overall the risk is minimal. Benefits include improved visualization of kidney lesions compared to non-contrasted ultrasound and the potential reduction of total lifetime load of gadolinium and improvement in cost-effectiveness.

2 Study Objectives

Primary Objective

To assess the agreement between CEUS and routine B-mode US for detecting indeterminate features of kidney lesions as graded on a Bosniak scale in patients with VHL under abdominal imaging surveillance.

Secondary Objective

[figure not shown]
To assess the agreement between CEUS and contrast-enhanced MRI for detecting indeterminate features of kidney lesions as graded on a Bosniak scale in patients with VHL under abdominal imaging surveillance.

3 Study Design

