3.2 Primary Study Endpoints

The primary study endpoint will be agreement of qualitative radiologist review of CEUS images with routine B-mode US.

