3.3 Secondary Study Endpoints

The secondary study endpoint will be agreement of qualitative radiologist review of CEUS images with contrast-enhanced MRI.

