7.1 Sample Size Determination

The goal of this feasibility study is to enroll a total of 15 subjects with familial syndrome at risk of kidney cancer, with at least 10 having 1 kidney lesion. This will yield up to 30 kidneys which will be assessed using CEUS, B-mode US and contrast MRI. Each of the 3 images on each kidney read by 3 readers with a Bosniak score assigned to each lesion. The primary objective is to assess agreement between the new imaging approach via CEUS with the most widely used existing technique, contrast-enhanced MRI, based on dichotomized Bosniak scores (I/II/IIF versus III/IV). A high kappa would warrant further investigation of CEUS as an alternative to MRI and other approaches. As described below in section 7.2, overall point estimates and confidence intervals will be computed for the kappa of interest based on averaging across the 3 readers. The proposed sample size will yield 95% confidence intervals with widths no greater than 0.30 over a wide range of true kappas, which should provide sufficient precision in kappa estimates to make a determination regarding feasibility of CEUS for future research.

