7.2 Statistical Methods

Kappas will be calculated separately for each reader for CEUS versus B-mode US, CEUS versus contrast MRI, and B-mode US versus contrast MRI, using the dichotomized Bosniak score. Confidence intervals for kappas will be computed by bootstrapping subjects, accounting for potential correlations of kidneys within subjects. Differences in agreement between readers will be based on comparing reader specific kappas, with statistical significance of these differences tested via bootstrapping. An overall kappa will be computed for each paired imaging comparison by averaging kappas across readers, with a 95% interval calculated via bootstrapping. Differences in overall kappas for the 3 paired imaging comparisons will be assessed using a bootstrap test. The above analyses will also be done separately for kidneys with lesions and without lesions, to evaluate whether agreement varies in these two important subgroups. Agreement between readers will be determined separately for each imaging modality by computing kappas for all pairs of readers, along with bootstrap confidence intervals. An overall assessment of reader agreement for each of the 3 modalities will be calculated by averaging the pairwise kappas. Finally, weighted kappa analyses will be done using the raw 5-point Bosniak scores, similar to those for the dichotomized Bosniak scores.

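### The plan declares two different primary comparisons (CEUS versus B-mode US, and CEUS versus contrast MRI) and does not say how a CEUS/B-mode kappa is to be read

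*Combined protocol and SAP*

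**What the plan says.** Section 2 states the primary objective as "To assess the agreement between CEUS and routine B-mode US for detecting indeterminate features of kidney lesions as graded on a Bosniak scale" and makes the same comparison against contrast-enhanced MRI the secondary objective. The endpoint sections agree with Section 2. Section 3.2: "The primary study endpoint will be agreement of qualitative radiologist review of CEUS images with routine B-mode US". Section 3.3: "The secondary study endpoint will be agreement of qualitative radiologist review of CEUS images with contrast-enhanced MRI".

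Section 7.1 says otherwise: "The primary objective is to assess agreement between the new imaging approach via CEUS with the most widely used existing technique, contrast-enhanced MRI". It goes on to say how the result would be used: "A high kappa would warrant further investigation of CEUS as an alternative to MRI and other approaches". It then claims 95% interval widths of at most 0.30 for the kappa of interest, averaged over 3 readers, with 15 subjects and up to 30 kidneys.

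Section 7.2 treats all pairs alike: "Kappas will be calculated separately for each reader for CEUS versus B-mode US, CEUS versus contrast MRI, and B-mode US versus contrast MRI". It adds: "Differences in overall kappas for the 3 paired imaging comparisons will be assessed using a bootstrap test". It does not name a primary pair.

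The Study Summary words the objective a third way, "To determine accuracy of CEUS for detection of malignancy kidney lesions in patients with Von-Hippel Lindau", and lists contrast-enhanced MRI as the reference.

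**The concern.** A study can have only one answer to the question of which comparison is primary, and this plan gives two. Three kappas will be computed on the same footing, and two of them have a claim in the text to be the headline. Whoever writes the report could justify either after seeing the results.

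The two candidates also differ in meaning. High agreement with MRI supports using CEUS in place of MRI, and Section 7.1 says so. Agreement with B-mode has no such reading. Section 1.2 says that ultrasound without contrast often cannot separate malignant from benign tumours, and Section 1.5 lists better visualisation than non-contrast ultrasound as a benefit of CEUS. High agreement with B-mode may then mean that contrast added nothing. Low agreement is not good news in itself either, because CEUS could differ from B-mode by being wrong. If the pair named in Sections 2 and 3.2 is reported as primary, the plan does not say which result would support further study.

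**Working it through.** **Step 1. Set the sections side by side.**

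| Place | CEUS vs B-mode | CEUS vs MRI |
|---|---|---|
| Section 2 | primary | secondary |
| Sections 3.2, 3.3 | primary | secondary |
| Section 7.1 | not mentioned as an aim | primary |
| Section 7.2 | analysed, no rank | analysed, no rank |
| Study Summary | not mentioned | MRI is the reference; objective is accuracy |

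The contradiction is settled by this table alone. The arithmetic below shows only whether the choice matters.

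**Step 2. How far apart can the two kappas be?** The documents give no prevalence of Bosniak III/IV and no B-mode accuracy, so these inputs are assumed. Take CEUS identical to MRI, so that its kappa with MRI is 1.00. Let p be the prevalence of III/IV on MRI, and Se and Sp the sensitivity and specificity of B-mode against MRI. Then:

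- observed agreement po = p·Se + (1−p)·Sp
- B-mode positive fraction m = p·Se + (1−p)(1−Sp)
- chance agreement pe = p·m + (1−p)(1−m)
- kappa(CEUS, B-mode) = (po − pe)/(1 − pe)

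Worked case, p 0.3, Se 0.5, Sp 0.95: po = 0.150 + 0.665 = 0.815; m = 0.150 + 0.035 = 0.185; pe = 0.0555 + 0.5705 = 0.626; kappa = 0.189/0.374 = 0.505.

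Over p 0.1-0.5, Se 0.3-0.7, Sp 0.9-1.0:

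- minimum 0.184 (p 0.1, Se 0.3, Sp 0.9)
- maximum 0.808 (p 0.1, Se 0.7, Sp 1.0)
- maximum 0.643 if Se is at most 0.5 (p 0.1, Se 0.5, Sp 1.0)

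If B-mode is close to MRI (Se 0.90-0.95, Sp 0.95-0.98), the range is 0.736 (p 0.1, Se 0.90, Sp 0.95) to 0.933 (p 0.4, Se 0.95, Sp 0.98).

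A perfect result under Section 7.1 can therefore look poor, moderate or good under Section 2.

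**Step 3. Does the choice change the number of kidneys?** B-mode is done at the CEUS visit (Sections 3.1 and 6.1), so up to 30 kidneys are available for that pair. MRI is collected only if done within 4 months before or after (Section 3.1, Appendix 1), an 8-month window. No study MRI is scheduled. If CEUS visits fall at random relative to clinical MRI:

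- MRI every 24 months (the VHL guideline interval in Section 1.1): 8/24 × 15 = 5 subjects = 10 kidneys
- MRI every 12 months: 8/12 × 15 = 10 subjects = 20 kidneys
- CEUS timed to the MRI: 15 subjects = 30 kidneys

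**Step 4. The 0.30 width.** It cannot be reproduced, because Section 7.1 gives no prevalence, no correlation between readers and no kappa range. As a guide, the large-sample standard error of a 2×2 kappa with equal marginals at prevalence 0.5 reduces to √((1−κ²)/n). For the mean of 3 independent readers the width is 2 × 1.96 × √((1−κ²)/n)/√3. This treats kidneys as independent and is favourable to the plan.

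| Kidneys | κ 0.6 | κ 0.7 | κ 0.8 |
|---|---|---|---|
| 30 | 0.33 | 0.30 | 0.25 |
| 20 | 0.40 | 0.36 | 0.30 |

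The formula is the same for either pair. The pair matters through its evaluable number and through the kappa expected for it.

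**The case against.** The strongest reply is that this is a 15-subject feasibility study with no success threshold and no alpha attached to the primary. All three kappas will be reported with the same estimator, dichotomisation and interval method, so no error rate is affected and no data are lost. B-mode versus MRI was never a candidate primary, so the choice is between two results. This is fair, and it limits the harm to how the result is labelled and read. It does not remove the contradiction: the primary result is what a pilot reports first and what the next study is built on.

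Second, Section 7.1 mentions other approaches besides MRI, which could include B-mode. That wording follows directly on the MRI objective and gives no direction or cut-off for B-mode. With Sections 1.2 and 1.5 expecting contrast to add information, it does not settle the reading.

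Third, the kappa ranges are wide and rest wholly on assumptions. That is so. They show that the two candidates need not agree, not that they will differ.

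Fourth, the 10-kidney figure is the pessimistic end. The Study Summary makes MRI surveillance a key inclusion criterion, Sections 3.1 and 4.3 speak of annual screening, and Section 7.1 expects every kidney to be read on all three modalities. These make fuller availability plausible. None of them guarantees an MRI inside the window, annual screening may mean ultrasound, and Section 4.1.4 does not require an MRI.

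Finally, preferring MRI is a judgement. Naming B-mode consistently would also cure the contradiction, provided its reading is stated.

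**Conclusion.** The concern holds. Sections 2, 3.2 and 3.3 contradict Section 7.1 on the primary comparison, Section 7.2 does not resolve it, and the CEUS/B-mode kappa has no stated favourable direction. This rests on the current text and on no assumption.

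The size of the consequence does depend on assumptions. With CEUS identical to MRI, the B-mode kappa could be anywhere from 0.18 to 0.81, or 0.74 to 0.93 if B-mode is nearly as good as MRI. Evaluable kidneys are up to 30 for the B-mode pair and about 10 to 30 for the MRI pair, depending on MRI interval and visit timing. Each kappa remains interpretable as an estimate. What is missing is one designated primary and, for the B-mode pair, a rule for reading it. This should be corrected before any images are read.

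**What to change.** Name one primary pair, in the same words, in the Study Summary and Sections 2, 3.2, 3.3, 7.1 and 7.2.

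- **Preferred:** CEUS versus contrast MRI, as the reader-averaged kappa on the dichotomised Bosniak score. It fits the rationale of replacing MRI, the Study Summary reference and Section 7.1. Make CEUS versus B-mode secondary, and read the added value of contrast as kappa(CEUS, MRI) minus kappa(B-mode, MRI), which the Section 7.2 bootstrap test of differences already covers. State how many kidneys are expected to have an MRI in the window and how those without one are handled.
- **If B-mode stays primary:** state whether high or low agreement supports further study and why, and rewrite Section 7.1 around that pair.
- **Either way:** re-derive the Section 7.1 interval width for the named pair and its evaluable number, with the assumed prevalence and reader correlation stated, rather than carrying over 0.30.

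The cost is wording in the Study Summary and five sections, a short recalculation, and submission of the amendment to the IRB under Section 11. No scans or reads are added, because Section 7.1 already has 3 readers score all three modalities. The drawback of an MRI primary is that kidneys without a clinical MRI within 4 months drop out of the primary analysis. Keeping B-mode avoids that loss but needs the stated reading.

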3.1 General Design

This study is a pilot cross-sectional study.

Study Schema:

Any patient with a familial syndrome at risk of kidney cancer (VHL, BHD, HLRCC or TSC) undergoing annual imaging screening is eligible, but we will target inclusion of at least 10 subjects who have at least 1 kidney lesion. Therefore, up to 5 subjects may have no current kidney lesions. Subject participation will be

only for the day of CEUS study. There will be no follow-up period for this study. However, if results are encouraging, a longitudinal observational study may follow, and these same subjects would be eligible for enrollment.

Abdominal imaging in patients with VHL is also used to monitor the pancreas. Although pancreatic lesions are less common than kidney lesions, cross-sectional imaging allows for monitoring of both organs. For patients with VHL, we will image the pancreas in addition the kidneys in order to establish parameters for pancreas CEUS. CEUS of the pancreas is not novel⁵¹, but its use for screening in patients at risk of pancreas lesions has not been investigated.

Following completion of imaging, all CEUS, MRI (within 4 months) and B-mode (at time of CEUS) US studies will be de-identified. Blinded radiologists will interpret images and provide an overall assessment of risk of malignancy to each kidney using the Bosniak criteria for each kidney lesion present. The Bosniak criteria places cystic lesions into one of 5 categories (I, II, IIF, III and IV) based on lesion characteristics. CEUS based diagnosis will be compared to the diagnoses on routine B-mode US and contrast-enhanced MRI.

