4.1.1 Able to provide written informed consent 

4.1.2 Willing to comply with protocol requirements 

4.1.3 At least 18 years of age

4.1.4 Carry a diagnosis of VHL, BHD, HLRCC or TSC and able to undergo routine clinical screening tests for RCC

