7.3 Subject Population(s) for Analysis

All subjects will be used for analysis.

8 Safety and Adverse Events

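### The objectives name VHL only, but four syndromes may enrol, all subjects are pooled and no VHL-only kappa is planned

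*Combined protocol and SAP*

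**What the plan says.** **Where the population is VHL only**
- The title describes CEUS as a "Screening Tool for Kidney Cancer in Patients with Von Hippel-Lindau".
- The objective in the Study Summary is "To determine accuracy of CEUS for detection of malignancy kidney lesions in patients with Von-Hippel Lindau".
- In Section 2, the primary objective (CEUS against B-mode US) and the secondary objective (CEUS against MRI) end with the same words: "for detecting indeterminate features of kidney lesions as graded on a Bosniak scale in patients with VHL under abdominal imaging surveillance".

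**Where it is four syndromes**
- Section 3.1: "Any patient with a familial syndrome at risk of kidney cancer (VHL, BHD, HLRCC or TSC) undergoing annual imaging screening is eligible".
- Section 4.1.4: "Carry a diagnosis of VHL, BHD, HLRCC or TSC and able to undergo routine clinical screening tests for RCC".
- The diagnosis row of the Study Summary also lists the other syndromes. Section 7.1 sizes the study at 15 subjects with a familial syndrome, not 15 with VHL.

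**Enrolment targets.** The only target concerns lesions: "we will target inclusion of at least 10 subjects who have at least 1 kidney lesion" (Section 3.1). No minimum is set for VHL and no limit for the others.

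**Analysis.** Section 7.3 states: "All subjects will be used for analysis". Section 7.2 plans kappas by reader, averaged over readers, and separately for kidneys with and without lesions. It plans nothing by syndrome.

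**Recruitment.** Section 4.3 names one source, the VHL Clinical Care Center, and gives 20 to 25 patients under annual screening. It does not divide them by syndrome.

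**The concern.** The objectives ask about agreement in VHL, while the analysis estimates agreement in whatever mix of syndromes enrols. Kappa depends on how often kidneys fall in Bosniak III/IV as well as on how well the methods agree. A different case mix in the other syndromes could therefore move the pooled value away from the VHL value, in either direction.

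Section 7.1 says that a high kappa would justify further study of CEUS as an alternative to MRI. A reader of that result needs to know which patients it describes. If the objectives stay as written, the natural reading will be VHL, and the planned tables would give no means of checking it.

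**Working it through.** **1. Is any planned analysis confined to VHL?** Setting Section 2 beside Sections 7.2 and 7.3, the answer is no. The lesion split is the only subgroup, and it cuts across syndromes.

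**2. Are non-VHL subjects actually foreseen?** Yes. Section 3.1 reserves pancreas imaging for subjects with VHL, and Section 5.2 allots a pancreas injection to VHL patients only. Neither provision would be needed if all subjects had VHL.

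**3. How far could pooling move kappa?** The documents give neither the syndrome mix nor any III/IV frequency. Section 1.1 gives cyst and RCC frequencies for VHL and none for the other syndromes. All inputs in this step are therefore assumptions, apart from 15 subjects with two kidneys each (Section 7.1).

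Kappa = (observed agreement − chance agreement) / (1 − chance agreement).

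*Illustration with counts.* Assume 10 VHL subjects (20 kidneys): 5 positive on both methods, 2 and 2 discordant, 11 negative on both.
- Observed = 16/20 = 0.800. Chance = (7/20)² + (13/20)² = 0.1225 + 0.4225 = 0.545. Kappa = 0.255/0.455 = 0.560.

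Add 5 non-VHL subjects whose 10 kidneys are all negative on both methods (5, 2, 2, 21).
- Observed = 26/30 = 0.867. Chance = (7/30)² + (23/30)² = 0.054 + 0.588 = 0.642. Kappa = 0.2244/0.3578 = 0.627.

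The shift is 0.07. If the ten added kidneys carry no lesion, the with-lesion kappa in Section 7.2 leaves them out, and their contribution disappears there. The plan does not say how a lesion-free kidney is scored, so counting it as negative is a further assumption.

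*Other assumed mixes.* The two groups' 2×2 tables, each with equal margins, are weighted by their share of the 15 subjects:

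| VHL: kappa, III/IV share | Others: kappa, III/IV share | 14 VHL of 15 | 12 | 10 |
|---|---|---|---|---|
| 0.6, 0.3 | 0.9, 0.3 | 0.62 | 0.66 | 0.70 |
| 0.8, 0.3 | 0.4, 0.3 | 0.77 | 0.72 | 0.67 |
| 0.6, 0.4 | 0.6, 0.05 | 0.61 | 0.64 | 0.65 |

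Check of the last cell. Discordance is 2p(1−p)(1−kappa), which is 0.192 in VHL and 0.038 in the others. Pooled discordance is (2/3)(0.192) + (1/3)(0.038) = 0.1407. Pooled p is (2/3)(0.4) + (1/3)(0.05) = 0.2833, so discordance expected by chance is 2(0.2833)(0.7167) = 0.4061. Kappa = 1 − 0.1407/0.4061 = 0.65. A difference in III/IV share alone thus moves the pooled value, even with equal kappas.

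The pooled kappa equals the VHL kappa if all 15 subjects have VHL, or if both kappa and III/IV share are the same in the two groups.

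**4. What does a VHL-only kappa cost in precision?** Section 7.1 states a 95% interval width of at most 0.30 over a wide range of true kappas. That figure cannot be reproduced, because the range, the III/IV share and the correlations are not given; the point does not depend on it. For scale, assume kappa 0.8, III/IV share 0.3 and independent kidneys. With equal margins the large-sample variance is

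(1−k)/n × [(1−k)(1−2k) + k(2−k)/(2p(1−p))].

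- 15 VHL subjects (n = 30): (0.2/30)(−0.12 + 0.96/0.42) = 0.01444, SE 0.120, width 3.92 × 0.120 = 0.47. This holds if the three readers are fully correlated. With independent readers it is 0.47/√3 = 0.27.
- 12 VHL subjects: 0.53 and about 0.30.
- 10 VHL subjects: 0.58 and 0.33.

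**The case against.** The strongest reply is that this is unrevised wording rather than a wrong analysis. Section 7.1 names the analysed population openly, Section 1.1 explains why the other three syndromes also need surveillance, and no section promises a kappa labelled as VHL. Recruitment is from a VHL clinic, so most or all subjects may have VHL. The illustrated shift rests on a chosen mix, part of it may already be handled by the lesion split, and 0.07 is less than a quarter of the 0.30 width that Section 7.1 claims. In a 15-subject pilot it could not be told apart from sampling error.

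Most of this stands. It limits the size of the problem and makes restating the objectives a full remedy. It does not close the gap:
- The clinic's patients are not divided by syndrome. Filling 15 places from 20 to 25 patients means enrolling 60% to 75% of them (15/25 and 15/20), and nothing bounds the non-VHL share.
- The lesion split does not remove a difference between syndromes among kidneys that do have lesions.

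A reader might go further and infer that the pooled kappa is not a VHL estimate, or that pooling inflates it. The documents support neither. If all 15 subjects have VHL, the pooled kappa is the VHL kappa. If they do not, the direction of any shift is unknown.

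**Conclusion.** The mismatch is plain on the face of the protocol: the objectives are for VHL, eligibility and analysis are for four syndromes, and no planned result is confined to VHL. The planned kappa answers a mixed-syndrome question whenever non-VHL subjects enrol.

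Its effect on the estimate cannot be sized from the documents. It is nil if every subject has VHL and probably small if nearly all do. With 10 VHL subjects of 15, the assumed scenarios move kappa by 0.05 to 0.13 in either direction. These show what is possible, not what is expected. This is a minor point, worth correcting because correction is nearly free.

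**What to change.** Choose one and write it in before the images are read.

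1. **Keep the VHL objectives.** Add to Section 7.2 that the kappas are also computed in VHL subjects alone, that the VHL-only value answers the Section 2 objectives, and that the pooled kappa and the number of subjects per syndrome are shown beside it. Cost: one extra row per table. The downside is a wider interval if non-VHL subjects enrol, by a factor of about √(15/m) with m VHL subjects: 1.12 for 12 and 1.22 for 10. If all enrolled subjects have VHL, the two rows coincide and nothing is lost.
2. **Keep the pooled analysis.** Restate the title, the summary objective and both Section 2 objectives for the four syndromes, and draw the conclusion for that population. Cost: wording only. Counts by syndrome should still be reported so that readers can judge the mix.

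Neither option changes eligibility, sample size or study procedures.
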